3.5.2. Analysis of Sex Differences in PK

This study was not designed to formally assess differences in PK by sex. During the course of this study, preclinical evidence suggestive of sex-based differences in PK became available (communication with Sponsor). To facilitate a descriptive comparison of PK by sex, select PK parameters will be summarized by dose, dose group, and sex (Table 24 and Table 25). Group 4 parameters will be summarized by condition and sex (Table 25). AUC $_{\tau}$, C_{max} and C_{trough} will also be presented graphically by dose, dose group, and sex in box plots for Groups 1, 2 and 3 (Figure 13, Figure 14, and Figure 15). Box plots of AUC $_{tast}$ and C_{trough} by dose, dose group, weight, and sex will also be presented for Groups 1, 2, and 3 (Figure 17, Figure 18,

and Figure 19). Scatter plots of AUC_{last} and C_{max} will be presented by weight, sex, and fed/fasted condition for Group 4 (Figure 20).

For the statistical models described in Sections 3.5.3 and 3.5.5, sex will be added as a covariate. The models with and without the additional covariate for sex will be compared, and the final model will be chosen based on Akaike Information Criterion (AIC) and graphical diagnostics of model assumptions and fit.

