2. CLINICAL STUDY METHODS

2.1. Treatment Groups

This Phase I study is an open label multiple ascending dose evaluation of the safety and PK of oxfendazole (3, 7.5, or 15 mg/kg) in healthy adult men and nonpregnant women aged 18-45 (inclusive) followed by a single dose crossover trial evaluating the safety and pharmacokinetics of a single dose of oxfendazole (3 mg/kg) given following an 8 hour fast or following a high fat meal.

In the multiple ascending dose trial, each dose group will be comprised of 8 subjects, all of whom will receive study product once daily for 5 days. To enhance safety, 1 sentinel subject will be enrolled and followed for 7 days for defined safety events. A second sentinel subject will then be enrolled and followed for 7 days. If no predefined safety events are identified, the remaining 6 subjects in this group will be enrolled. All volunteers will be followed for 10 days and PK, safety laboratory and EKG studies will be performed. If no predefined safety events occur after all 8 subjects have completed the Day 10 visit, the DMID Medical Monitor will issue approval to proceed with enrollment of the second group of 8 subjects, who will receive 5 days of 7.5 mg/kg of oxfendazole using the same enrollment plan as outlined above. If no predefined safety events are encountered, the third group of 8 subjects will be enrolled to receive 5 days of 15 mg/kg using the same enrollment plan.

In the second phase of the study evaluating the effects of food on drug absorption, 12 subjects will be enrolled into a randomized, single dose, two-period, two-treatment (2x2) crossover trial. In the first period of this trial, half of the subjects will initially receive a single dose of 3 mg/kg of oxfendazole following an 8 hour fast, and the other half will receive a single dose of 3 mg/kg of oxfendazole following a high fat breakfast. After a one-week wash-out period, subjects will cross over in the second period to receive a single dose following a high fat breakfast or 8 hour fast. The order of conditions, Sequence A (fasted condition first) and Sequence B (fed condition first), will be randomly assigned upon enrollment in a 1:1 ratio.

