3.5.3. Attainment of Steady State

Attainment of steady state by Dose 5 will be assessed by visual examination of the concentration versus time plots (Figure 1, Figure 2, Figure 3, Figure 4, Figure 5, and Figure 6).

Graphical findings will be supported by statistical comparison of C_{max} and C_{trough} values on Day 5 with the corresponding values on Day 4 and Day 3. C_{max} and C_{trough} will be log-transformed and analyzed using the following mixed effects model for Y_{ijk} , the log-transformed exposure parameter observed on the kth subject on day j of dose group i:

$$Y_{ijk} = \mu + \pi_j + \lambda_i + \tau_{d[i,j]} + s_{ik} + \varepsilon_{ijk}$$

where μ is the intercept; π_j is a fixed effect associated with day j; λ_i is a fixed effect associated with dose group i, $\tau_{d[i,j]}$ is a fixed effect associated with the interaction of day j and dose group i; s_{ik} is a random effect associated with the kth subject in dose group i, and e_{ijk} is a random error term with mean 0 and variance σ_e^2 . This model will be fit using restricted maximum likelihood estimation (REML) in SAS PROC MIXED, with the Kenward and Roger denominator degrees of freedom. Covariance structure will be selected based on AIC, from the following candidate structures: variance components, first-order autoregressive, compound symmetry, Toeplitz, and unstructured. SAS code will be similar to:

PROC MIXED;

CLASS DAY DOSEGROUP SUBJECT;

MODEL LCMAX = DAY DOSEGROUP DAY*DOSEGROUP / DDFM=KR;

RANDOM SUBJECT / TYPE = VC;

LSMEANS DAY*DOSEGROUP / PDIFF CL;

RUN;

The mean difference in log-transformed parameter (C_{max} or C_{trough}) between Day 5 and each of Days 4 and 3 at each dose level will be back transformed to obtain the geometric mean ratio. Contrasts of model parameters will be used to generate 95% confidence intervals for the geometric mean ratios. The geometric mean ratios and corresponding confidence intervals will be graphically depicted in Figure 25 and reported in Table 26, alongside the p-value for the hypothesis test of no difference in log-transformed C_{max} and C_{trough} between Day 5 and each of Days 4 and 3 at each dose level.

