3.5.5. Analysis of Dose Proportionality

The presence of dose proportionality over the range of studied dose levels for Groups 1-3 will be assessed using the exposure parameters AUC_{τ} , C_{max} , and C_{trough} of Dose 1 and at expected steady-state (Dose 5). Analysis will be conducted with the power model as described by Smith et al²:

$$AUC_{\tau} = e^{\alpha} \times dose^{\beta}$$
.

Let ρ be the ratio (highest dose studied / lowest dose studied) and let (L, U) represent the 90% confidence interval for $\hat{\beta}$. In the presence of dose proportionality, $\rho^{\hat{\beta}-1}=1$. Accordingly, using the bioequivalence criteria of the current FDA guidance³, dose proportionality across the studied dose range is concluded when:

$$\Theta_l = 0.8 \le \rho^{L\text{-}1} < \rho^{U\text{-}1} \le 1.25 = \Theta_h.$$

Or, equivalently,

$$1 + \frac{\ln 0.8}{\ln \rho} \le L < U \le 1 + \frac{\ln 1.25}{\ln \rho}.$$

Dose proportionality using C_{max} and C_{trough} will also be assessed using the same approach. Point estimates and 90% confidence intervals for $\hat{\beta}$ will be presented (Table 28). Predicted values from the power model including 90% prediction bands will be overlaid on plots of exposure data (AUC_{\tau}, C_{max}) by dose in mg/kg (Figure 21, Figure 22). Additionally, ANOVA on the log-transformed parameters will be used to construct confidence intervals of the geometric means of dose-adjusted AUC_{\tau} and C_{max} by dose, which will be displayed in Table 29 and plotted side-by-side in order of increasing dosage (Figure 23, Figure 24).

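### SAP 3.5.2 uses AIC to decide whether sex stays in the steady-state model, but that model is fitted by REML, whose likelihoods are not comparable when the fixed effects differ

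*SAP*

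**What the plan says.** SAP 3.5.2 (Analysis of Sex Differences in PK): "For the statistical models described in Sections 3.5.3 and 3.5.5, sex will be added as a covariate". The fits with and without sex are then compared, and "the final model will be chosen based on Akaike Information Criterion (AIC) and graphical diagnostics of model assumptions and fit".

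SAP 3.5.3 (Attainment of Steady State): "This model will be fit using restricted maximum likelihood estimation (REML) in SAS PROC MIXED". The fixed effects are given in the code as "MODEL LCMAX = DAY DOSEGROUP DAY*DOSEGROUP / DDFM=KR". The target is a "statistical comparison of C_{max} and C_{trough} values on Day 5 with the corresponding values on Day 4 and Day 3".

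SAP 3.5.3 also uses AIC for a second purpose: "Covariance structure will be selected based on AIC, from the following candidate structures".

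SAP 3.5.5 (Analysis of Dose Proportionality): "Analysis will be conducted with the power model". No estimation method is named there.

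The SAP does not say that the sex comparison will use ML, how sex will be coded, or how AIC and the diagnostics will be weighed against each other.

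**The concern.** Choosing a covariance structure by REML AIC is sound, because every candidate has the same fixed effects. Choosing whether to include sex is a different task, because the two candidates differ in a fixed effect. The REML criterion contains a term that depends on the fixed-effects design matrix, and adding a column changes that term by an amount unrelated to how well sex explains the data. The two AIC values are then not on the same scale.

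At stake is which model the report calls final. SAP 3.5.2 says the sex work was prompted by preclinical evidence that emerged during the study. A reader may therefore take the presence or absence of sex in the final model as information about that signal.

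**Working it through.** The plan gives no figure for this comparison, so there is none to reproduce.

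**Inputs from the SAP.** "In the multiple ascending dose trial, each dose group will be comprised of 8 subjects" (2.1), so three groups give 24 subjects. Days 3, 4 and 5 give 24 × 3 = 72 observations per parameter. Day, dose group and their interaction use 9 fixed-effect parameters, or 10 with a sex main effect.

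**Assumed, because the documents give no values.** Between-subject CV 20–100%; within-subject CV 15–30%; four women per group of eight (two as a variant); random-intercept covariance. REML AIC is taken to penalise covariance parameters only, so its difference equals the difference in −2 restricted log-likelihood.

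**Criterion.** −2RLL = log|V| + log|X′V⁻¹X| + r′V⁻¹r + (n − p) log(2π).

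**Effect of coding.** Multiplying the sex code by c shifts the REML comparison by 2 ln(c) and leaves the ML comparison unchanged. In one simulated data set, adding sex changed the criteria as follows:

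| Coding of sex | Change in −2RLL | Change in −2 log L (ML) |
|---|---|---|
| 0/1 or 1/2 | +2.14 | −0.54 |
| −1/+1 | +3.53 | −0.54 |
| 0/10 | +6.75 | −0.54 |

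The steps agree with the formula: 2 ln 2 = 1.39 and 2 ln 10 = 4.61.

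**Effect of between-subject variance.** If the variances were known, REML AIC would keep sex when its chi-square statistic (1 df) exceeds ln(I / 2π), where I is the information on the sex coefficient. With 0/1 coding and four women per group, the squared deviations of the code sum to 24 × 0.25 = 6. So I = 6 / (σ_b² + σ_w²/3), with each σ² = ln(1 + CV²). Coding −1/+1 multiplies I by 4 and raises the threshold by ln 4 = 1.39.

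| CV between / within | σ_b² + σ_w²/3 | Threshold, 0/1 | P(χ² > threshold) | Simulated, 0/1 | Simulated, −1/+1 |
|---|---|---|---|---|---|
| 20% / 15% | 0.0392 + 0.0074 = 0.0466 | 3.02 | 8% | 8% | 4% |
| 40% / 20% | 0.1484 + 0.0131 = 0.1615 | 1.78 | 18% | 21% | 9% |
| 60% / 30% | 0.3075 + 0.0287 = 0.3362 | 1.04 | 31% | 30% | 11% |
| 100% / 30% | 0.6931 + 0.0287 = 0.7219 | 0.28 | 60% | 65% | 22% |

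The simulated columns are the share of 600 trials of the full 24 × 3 model, with no sex effect, in which sex is kept (Monte Carlo error about 2 points). With two women per group, 0/1 coding gives 10%, 25% and 38% at CVs of 20%, 40% and 60%.

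**ML for comparison.** ML AIC with sex counted as a parameter keeps it in 19–23% of trials in every null scenario. As a check on subject means, sex is kept when 24 ln(1 + F/20) > 2, that is F > 20(e^(2/24) − 1) = 1.74. P(F(1,20) > 1.74) is about 20%, and neither the coding nor the variance enters.

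**Response to a true effect** (CV 40%/20%, four women per group; share of trials keeping sex):

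| True female/male ratio | REML AIC, 0/1 | REML AIC, −1/+1 | ML AIC |
|---|---|---|---|
| 1.0 | 21% | 9% | 23% |
| 1.25 | 53% | 32% | 53% |
| 1.5 | 87% | 74% | 89% |

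**Effect on the steady-state result.** With complete data the group 1 day contrasts were −0.1643 and −0.0360 (SE 0.0878 each), identical with and without sex. With 6 missing values, the Day 5 versus Day 3 estimates moved by at most about 0.02 log units.

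**The case against.** The case for leaving the text alone has several parts.

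- **The selection still follows the evidence.** This stands. A reader might infer that the choice reflects scaling instead of any sex effect. The last table rules that out: at CV 40% with 0/1 coding, REML and ML AIC behave almost alike. What is arbitrary is the threshold.
- **Log base.** A reader might infer that the choice between ln and log10 leaves the decision open, since a change of base would shift the REML comparison by 2 ln(ln 10) = 1.67. The documents do not support that. The power model in 3.5.5 is written with e and ln, and the CV formulas in 3.5.7 hold only for natural logs. Nothing suggests log10.
- **Diagnostics are also named.** True, so AIC is not the sole rule. But their weight is not stated, and AIC is the only numerical criterion.
- **ML is not ruled out.** Also true: 3.5.2 does not name the likelihood. But the only estimation method given for this model is REML, and AIC is already applied to that fit in 3.5.3. An analyst following the text would compare REML fits.
- **No planned result depends on it.** This largely stands. Table 26 and Figure 25 report the day ratios, and the by-sex summaries (Tables 23–25) are descriptive. No planned table reports a sex coefficient.
- **The power model.** A reader might extend the point to the 90% interval for the dose slope in 3.5.5. The SAP names neither REML nor a random effect there, so that extension is only conditional.

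**Conclusion.** The rule as written is not valid for the 3.5.3 model, because it compares REML-based AIC values between models with different fixed effects. With 0/1 coding and no sex effect, the chance of keeping sex runs from about 8% to 30% as the assumed between-subject CV goes from 20% to 60%, against a steady 19–23% under ML. Changing the coding from 0/1 to −1/+1 moves the comparison by 1.39 AIC units.

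These sizes rest on the assumed CVs, the assumed sex split and an AIC penalty that counts covariance parameters only. Counting sex as well would add a constant 2 and would not remove the dependence on coding or variance.

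The practical consequence is small. It concerns which model is called final, and the steady-state ratios hardly depend on that: not at all with complete data and a sex main effect, and slightly with missing samples. A sex-by-day term could change this, but 3.5.2 describes only a covariate. The AIC choice of covariance structure is unaffected. The dose-slope interval in 3.5.5 comes into question only if that model is also fitted by REML.

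**What to change.** Add one sentence to SAP 3.5.2: models with and without sex (3.5.3, and 3.5.5 if fitted in a REML procedure) will be compared by AIC under METHOD=ML on the same data, with sex counted as a parameter; the chosen 3.5.3 model will then be refitted by REML for the reported estimates and intervals.

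Stating how sex is coded is good practice, although the ML comparison does not depend on it. The cost is the sentence and an ML run of each candidate model. The design, data collection and planned tables do not change.

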3.5.3. Attainment of Steady State

Attainment of steady state by Dose 5 will be assessed by visual examination of the concentration versus time plots (Figure 1, Figure 2, Figure 3, Figure 4, Figure 5, and Figure 6).

Graphical findings will be supported by statistical comparison of C_{max} and C_{trough} values on Day 5 with the corresponding values on Day 4 and Day 3. C_{max} and C_{trough} will be log-transformed and analyzed using the following mixed effects model for Y_{ijk} , the log-transformed exposure parameter observed on the kth subject on day j of dose group i:

$$Y_{ijk} = \mu + \pi_j + \lambda_i + \tau_{d[i,j]} + s_{ik} + \varepsilon_{ijk}$$

where μ is the intercept; π_j is a fixed effect associated with day j; λ_i is a fixed effect associated with dose group i, $\tau_{d[i,j]}$ is a fixed effect associated with the interaction of day j and dose group i; s_{ik} is a random effect associated with the kth subject in dose group i, and e_{ijk} is a random error term with mean 0 and variance σ_e^2 . This model will be fit using restricted maximum likelihood estimation (REML) in SAS PROC MIXED, with the Kenward and Roger denominator degrees of freedom. Covariance structure will be selected based on AIC, from the following candidate structures: variance components, first-order autoregressive, compound symmetry, Toeplitz, and unstructured. SAS code will be similar to:

PROC MIXED;

CLASS DAY DOSEGROUP SUBJECT;

MODEL LCMAX = DAY DOSEGROUP DAY*DOSEGROUP / DDFM=KR;

RANDOM SUBJECT / TYPE = VC;

LSMEANS DAY*DOSEGROUP / PDIFF CL;

RUN;

The mean difference in log-transformed parameter (C_{max} or C_{trough}) between Day 5 and each of Days 4 and 3 at each dose level will be back transformed to obtain the geometric mean ratio. Contrasts of model parameters will be used to generate 95% confidence intervals for the geometric mean ratios. The geometric mean ratios and corresponding confidence intervals will be graphically depicted in Figure 25 and reported in Table 26, alongside the p-value for the hypothesis test of no difference in log-transformed C_{max} and C_{trough} between Day 5 and each of Days 4 and 3 at each dose level.

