Table 25: Summary Statistics of PK Parameters by Group and Sex: Group 4

| Statistics | AUC _{last} | | T _{max} | | | max g/mL) | t _{1/2} | |
|------------|---------------------|--------|------------------|--------|------|--------------|------------------|--------|
| | Male | Female | Male | Female | Male | Female | Male | Female |
| Fed | | | | | | | | |
| N^1 | X | X | X | X | X | X | X | X |
| Mean | X.X | X.X | X.X | X.X | X.X | X.X | X.X | X.X |
| SD | X.X | X.X | X.X | X.X | X.X | X.X | X.X | X.X |
| Min | X | X | X.X | X.X | X | X | X.X | X.X |
| Median | X | X | X.X | X.X | X | X | X.X | X.X |
| Max | X | X | X.X | X.X | X | X | X.X | X.X |
| CV % | X | X | X | X | X | X | X | X |
| GM | X.X | X.X | X.X | X.X | X.X | X.X | X.X | X.X |
| Fasted | | | | | | | | |
| N^1 | X | X | X | X | X | X | X | X |
| Mean | X.X | X.X | X.X | X.X | X.X | X.X | X.X | X.X |
| SD | X.X | X.X | X.X | X.X | X.X | X.X | X.X | X.X |
| Min | X | X | X.X | X.X | X | X | X.X | X.X |
| Median | X | X | X.X | X.X | X | X | X.X | X.X |
| Max | X | X | X.X | X.X | X | X | X.X | X.X |
| CV % | X | X | X | X | X | X | X | X |
| GM | X.X | X.X | X.X | X.X | X.X | X.X | X.X | X.X |

Number of data points used to compute the summary statistics. BQL values were imputed as 0 if they did not come after a PK sample concentration that is above the LLOQ and treated as missing otherwise.

Table 26: Statistical Analysis of Attainment of Steady State

| Exposure | Dose | Day 3 vs. Day 5 Comp | arison¹ | Day 4 vs. Day 5 Comparison ¹ | | |
|--------------------------|-----------|----------------------------------|---------|---|---------|--|
| Parameter | Level | Geometric Mean Ratio (95% CI) | p-value | Geometric Mean Ratio (95% CI) | p-value | |
| | 3 mg/kg | x.xxx (x.xxx, x.xxx) | X.XXX | x.xxx (x.xxx, x.xxx) | X.XXX | |
| C _{max} (ng/mL) | 7.5 mg/kg | x.xxx (x.xxx, x.xxx) | X.XXX | x.xxx (x.xxx, x.xxx) | X.XXX | |
| | 15 mg/kg | x.xxx (x.xxx, x.xxx) | x.xxx | x.xxx (x.xxx, x.xxx) | x.xxx | |
| | 3 mg/kg | x.xxx (x.xxx, x.xxx) | X.XXX | x.xxx (x.xxx, x.xxx) | X.XXX | |
| $C_{trough}(ng/mL)$ | 7.5 mg/kg | x.xxx (x.xxx, x.xxx) | x.xxx | x.xxx (x.xxx, x.xxx) | X.XXX | |
| | 15 mg/kg | x.xxx (x.xxx, x.xxx) | X.XXX | x.xxx (x.xxx, x.xxx) | X.XXX | |

¹Based on a mixed effects model with fixed effects of day, dose group, and day*dose group interaction, and random effect of subject.

Table 27: Population Summary Statistics for Accumulation Ratio

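### SAP 3.5.3 puts its candidate covariance structures on subjects rather than on days within a subject, so correlation that depends on the lag between days cannot be fitted as written

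*SAP*

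**What the plan says.** SAP 3.5.3 judges attainment of steady state by eye from the concentration plots and supports this with a model that compares Cmax and Ctrough "values on Day 5 with the corresponding values on Day 4 and Day 3".

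- **Model.** The fixed effects are day, dose group and their interaction. The subject term s_ik "is a random effect associated with the kth subject in dose group i"; the residual "is a random error term with mean 0 and variance" σ_e². No correlation between a subject's residuals on different days is written down.
- **Fit.** REML in PROC MIXED, "with the Kenward and Roger denominator degrees of freedom".
- **Covariance.** "Covariance structure will be selected based on AIC, from the following candidate structures: variance components, first-order autoregressive, compound symmetry, Toeplitz, and unstructured". The text does not say which matrix the structure applies to.
- **Code.** The only line with a TYPE= option is "RANDOM SUBJECT / TYPE = VC". It has no SUBJECT= option, and there is no REPEATED statement. The code is offered as indicative.
- **Output.** "Contrasts of model parameters will be used to generate 95% confidence intervals for the geometric mean ratios"; these go to Table 26 and Figure 25. The Table 26 footnote describes the model as having "fixed effects of day, dose group, and day*dose group interaction, and random effect of subject".

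The text does not say whether the model takes Days 3-5 only or all five days.

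**The concern.** First-order autoregressive and Toeplitz structures make sense only for ordered measurements, so the list is evidently meant for days within a subject. Placed on RANDOM SUBJECT without SUBJECT=, TYPE= instead describes the covariance matrix of the 24 subject effects. The AIC step then compares models that differ only in how different subjects relate to each other, and it cannot reach the model it was written to find.

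If adjacent days are more alike than days two apart, an exchangeable model gives both comparisons the same average standard error. That is too small for Day 5 v Day 3 and too large for Day 5 v Day 4. On the Day 4 comparison, a real rise is then more easily missed and the lack of significance read as steady state. Table 26 and Figure 25 are the section's only inferential outputs, and CLss/F in SAP 3.4 treats Dose 5 as expected steady state.

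**Working it through.** The plan states no figure to reproduce here.

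**Inputs.** 3 groups of 8 subjects, so 24 subjects (SAP 2.1); model, code and 95% level from SAP 3.5.3. Assumed: AR(1) residual correlation ρ between days, over the range 0.2 to 0.9, with equal variances and complete data. The documents give no value of ρ. The days modelled are taken first as Days 3-5 (24 × 3 = 72 observations), then as Days 1-5 (24 × 5 = 120).

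**Step 1: what each candidate does as coded.** The covariance is V = ZGZ′ + σ_e²I, with G the 24 × 24 matrix of subject effects.
- VC: one intercept variance. This is the usual random-intercept model.
- CS: adds the same covariance between all pairs of subjects. That amounts to a common random shift, which the fixed effects absorb, so REML cannot estimate it.
- AR(1) and Toeplitz: relate subjects according to their order in the data.
- UN: 24 × 25 / 2 = 300 parameters, from 72 or 120 observations.

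Under all five, a subject's Day 3-Day 4 and Day 3-Day 5 covariances are equal. The subject effect cancels in a within-subject difference. Generalised least squares with each G in turn (Days 3-5) gives the same variance for Day 5 − Day 3: 2σ_e²/8 = 0.25σ_e².

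**Step 2: size if residuals are AR(1).** The fitted residual variance averages 1 − ρ^lag over all pairs of modelled days. With three days (two pairs at lag 1, one at lag 2) the average is 1 − (2ρ + ρ²)/3. Hence

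model SE / true SE = √{[1 − (2ρ + ρ²)/3] / (1 − ρ^lag)},

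with lag 2 for Day 5 v Day 3 and lag 1 for Day 5 v Day 4. At ρ = 0.5 the average is 1 − 1.25/3 = 0.583. The ratios are √(0.583/0.75) = 0.882 and √(0.583/0.5) = 1.080. With five days at ρ = 0.5 the average is (4×0.5 + 3×0.75 + 2×0.875 + 0.9375)/10 = 0.694, and the ratios are 0.962 and 1.178.

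Coverage of nominal 95% intervals, from 40,000 simulated trials per row with pooled residual df 21 × (days − 1), that is 42 or 84 (simulation error about 0.15 points):

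| ρ | Days 3-5: 5 v 3, SE ratio / coverage | Days 3-5: 5 v 4 | Days 1-5: 5 v 3 | Days 1-5: 5 v 4 |
|---|---|---|---|---|
| 0 | 1.000 / 95.0% | 1.000 / 95.1% | 1.000 / 95.2% | 1.000 / 95.0% |
| 0.2 | 0.943 / 93.5% | 1.033 / 95.6% | 0.972 / 94.3% | 1.064 / 96.4% |
| 0.5 | 0.882 / 91.8% | 1.080 / 96.5% | 0.962 / 94.0% | 1.178 / 97.9% |
| 0.7 | 0.852 / 90.8% | 1.111 / 96.7% | 0.971 / 94.2% | 1.265 / 98.5% |
| 0.9 | 0.827 / 89.8% | 1.140 / 97.3% | 0.988 / 94.7% | 1.362 / 99.1% |

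**Step 3: structure placed on days.** Unstructured covariance on days was computed as the equivalent paired-difference interval with 21 df. Day 5 v Day 3 coverage returns to 94.9-95.2% at every ρ. With Days 3-5, mean Day 5 v Day 3 width relative to the coded model is 1.09, 1.16 and 1.24 at ρ = 0.2, 0.5 and 0.9. With Days 1-5 it is 1.07, 1.08 and 1.05. At ρ = 0 the relative width is 1.02 (Days 3-5) or 1.04 (Days 1-5).

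**The case against.** **The quoted line is itself legitimate.** A random intercept with TYPE=VC matches the displayed equation and the Table 26 footnote, and it already gives equal correlation among a subject's days. This stands. A reader might infer that the model ignores within-subject correlation or that the code is invalid; neither follows. Only lag-dependent correlation is missing.

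**The code is only indicative.** A programmer could add a REPEATED statement, the unworkable 300-parameter option would probably expose the slip, and the SAP preface allows justified deviations to be described in the report. So it is too much to say that serial correlation can never be fitted. But equation, code and footnote agree with one another, and none places a structure on days. Nothing pre-specified tells the programmer to do so.

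**The size is uncertain.** This stands. A reader might take the 90% figure as the expected coverage. It needs both a high ρ and a model limited to Days 3-5, and the documents support neither. The half-life of 8.5-11 h (protocol 2.1.2) leaves 2^(−24/8.5) = 14% to 2^(−24/11) = 22% of drug at 24 h. That does not fix ρ, but it gives no support for 0.7-0.9.

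**Cmax is not the same measure on each day.** SAP 2.3 schedules one post-dose sample on Days 3 and 4 but a full profile on Day 5. Equal-variance AR(1) data do not represent this, and no choice of covariance repairs it. This stands as a limit on the simulation.

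**A bare REPEATED line has its own costs.** It removes s_ik from the stated model, and AR(1) alone forces correlation towards zero with lag. True, so the equation must change too. Toeplitz on days includes a random intercept plus AR(1), and UN includes every candidate.

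**The stakes are low.** Steady state is assessed visually, no acceptance limit is tied to these intervals, and protocol 11.1 calls multi-dose kinetics descriptive. This limits severity but does not remove the error.

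**Conclusion.** The covariance selection is misplaced as written. The candidates act on covariance between subjects, so the AIC step cannot serve its evident purpose. That conclusion needs no assumption about ρ.

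The effect on the intervals does need one. For ρ from 0.2 to 0.9, the coverage loss for Day 5 v Day 3 is about 1.5 to 5 points if only Days 3-5 are modelled, and about 1 point or less if Days 1-5 are. Day 5 v Day 4 intervals over-cover by about 0.6 to 2.3 points or 1.4 to 4.1 points respectively. If there is no lag-dependent correlation, the coded VC model covers correctly.

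A reader might go on to infer that the steady-state conclusion is unsound. The documents do not support that: the analysis is secondary and supports a graphical judgement. The point should be corrected before analysis, but it does not threaten the trial's primary results.

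**What to change.** 1. State which days enter the model.
2. Replace the RANDOM line with `REPEATED DAY / SUBJECT=SUBJECT(DOSEGROUP) TYPE=<structure>;` and keep DDFM=KR.
3. Select by AIC among CS, AR(1), Toeplitz and UN on days within subject. CS retains the equal within-subject correlation of the present model. VC drops out because on days it would mean no within-subject correlation at all. Alternatively, pre-specify UN: 3 × 4 / 2 = 6 parameters for Days 3-5, or 5 × 6 / 2 = 15 for Days 1-5.
4. Revise the model equation (s_ik and the residual) and the Table 26 footnote to match.

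The cost is a small text and code change with no new data. Under UN, intervals are about 2-4% wider if there is no serial correlation.
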